The BSE may not accurately diagnose aspiration in ARF survivors. By combining specific components of the BSE, clinical prediction rules (CPRs) have been developed for patients with head and neck cancer or cerebrovascular accidents.^{16-18;31;62-70} These disease-specific CPRs may not accurately detect aspiration in ARF survivors for the following reasons. 1) The proposed mechanisms responsible for aspiration in ARF survivors increase the likelihood of silent aspiration that would not be routinely detected on a BSE.^{9;59-61} 2) Decreased saliva production after radiation alters swallowing function and has been included in head and cancer specific CPRs.^{12-14;20;66;71} This criterion would most likely not contribute to aspiration in ARF survivors. 3) Some aspiration CPRs were developed using only patients referred for formal swallowing evaluations; creating both a selection bias and limiting generalizability of the results.^{69;70;72} 4) Due to their diminished respiratory reserve, the consequences of aspiration are greater in ARF survivors.⁷³ Therefore CPRs might need to be more sensitive for the detection of aspiration. 5) Certain CPRs were developed without comparison to a gold standard test of aspiration such as a VFSS or FEES.^{69;70;72} 6) The 3 ounce water swallow test (3-WST) is a sensitive initial screening test in hospitalized patients. However, it is unclear whether the 3-WST applies to ARF survivors, or what BSE components could be combined with the 3-WST to confirm aspiration.⁷⁴⁻⁷⁶

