Obtaining informed consent is a process that is reviewed by the appropriate members of our research team on a monthly basis. All of the personnel involved in screening and patient identification have successfully completed the on-line course on the Responsible Conduct of Research. Informed consent will be obtained from each patient or legally authorized representative (LAR) prior to enrollment in the trial. No study procedures will be done prior to obtaining informed consent. Permission to approach patients and/or LARs will be requested from the attending physicians.

In general our methods for obtaining informed consent include the following: 1. identification and contact of appropriate parties to perform informed consent, 2. arrangement of a mutually acceptable meeting time with this party in a private conference room or in the patient's room, and 3. a lengthy discussion between the study investigator and the interested party. The discussion includes an update of the patient's overall condition justifying the rationale for inclusion of the patient into the specific trial. The consent form is reviewed in detail including the background information and rationale regarding the specific intervention of the study, potential risks and options. Patients or their representatives are informed of their rights as a research subject and are informed of their ability to discontinue study participation at any time throughout the trial. Subjects or their representatives are given the opportunity to ask any questions regarding the verbally described consent form. Following this discussion, opportunity is given to privately read the consent form. If the patient or representative is illiterate, the consent form is read to them. After sufficient time, an additional question and answer session is performed if needed.

A few key points to the informed consent process.

1. Sit down when you are talking to the patient and/or surrogate.
2. Explain who you are and that you normally work with patients in the intensive care unit.
3. Explain that you are here to help determine if the patient is swallowing normally.
4. Explain that difficulty swallowing is common after being on a breathing machine

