5. State that the standard tests to determine whether someone can swallow properly after being on a breathing machine are to have a nurse or speech therapist to observe a person swallow liquids and foods of different consistencies. However, these tests are not perfect. Sometimes it appears that the patient can eat normally, and they are actually swallowing things down the wrong tube (into their lungs). Other times, it appears that the patient is not swallowing properly when they actually are swallowing properly.
6. In addition to this normal swallowing exam, there is an additional simple test we can do that is above and beyond the normal swallowing exam. This additional technique will definitively identify if someone is swallowing normally, and allow us to identify the correct strategy for eating. Sometimes we do this test as part of the normal patient swallowing evaluation.
7. The test is simple and done right here in the patient's room. It takes 5-10 minutes and the patient can watch the test if they want. We will put a very small tube (like a very thin straw) down the back of the throat so we can see your vocal cords. We will then have you swallow liquids and foods of different consistencies and see if the material is actually going down the wrong tube.
8. Share these results with your doctors so they have the additional information and can use the information to potentially take better care of you in regard to your feeding and swallowing.

If the patient agrees to the study, then the coordinator should contact the SLP who will perform the BSE, and the second SLP who will perform the FEES.

STUDY PROCEDURES:

1. Baseline assessments:

This information will be collected by the study coordinator at the time of enrollment.

Patient Age
Patient Gender
Patient Race
Patient Height
Patient Weight
Primary Service
Hospital Admission Date
ICU Admission Date
Intubation Date and Time
Size of the Endotracheal Tube
Extubation Date and Time
Previous reintubation (y/n)
APACHE II score
Charlson Comorbidity Index

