Next, a SLP will perform a comprehensive BSE on each ARF survivor, and a second blinded SLP will perform the FEES to determine whether aspiration is truly present. The order of the BSE and FEES exams will be randomized. The reason for the random order of the tests is that after several swallows, a patient who has not eaten orally in several days or weeks will start to do better as the system "wakes up". If the BSE always precedes the FEES, it might lead to a false result – it would show more aspiration on the BSE than the FEES. But it won't be because the BSE was showing a false positive; in fact it is just that the patient started to improve by the time he got the second exam.

2. Bedside Evaluation:

The BSE protocol should be performed within 24 hours from the time that the informed consent was signed. The BSE protocol will be performed in the same order and the amount of each bolus delivered in the exact manner for all patients. Unless there are medical restrictions (due to femoral lines, sacral wounds, etc), all BSEs should be performed in a sitting position. The SLP will document the patient position that the BSE was

performed.

Part 1: Initial Assessment: The SLP will review the subject's medical record and become knowledgeable with the patient's medical history. The patient should be seated with the head of the bed as elevated as possible. A physical exam of the aerodigestive system will be performed including respiratory rate; saliva formation; lip seal; tongue movement, strength, and coordination; palate movement, gag reflex; cough reflex; and voice quality/dysphonia. In addition, the SLP will also determine cough strength in L/min using a peak flow meter (HealthScan, Cedar Grove, NJ).

Part 2: Standardized consistency testing: The SLP will then administer five standard consistencies.¹⁰⁶ Some consistencies will be tested twice with different amounts. In general, the bolus should be administered with a medicine cup. A straw should only be used for the 3 ounce water test and the 2 ounce patient controlled trials.

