Part 3: Three Ounce Water Swallow Test (3-WST): During the standardized 3-WST, patients receive three ounces of water and are instructed to drink the entire amount, via cup or straw, completely and without interruption (the cup can be held to the patient's mouth by the SLP).^{74;76;109} The 3-WST will be scored as pass/fail. Criteria for failure of the 3-WST are: the inability to drink the entire amount, coughing or choking up to 1 minute after completion, or the presence of a wet-hoarse vocal quality.

At this point the SLP will document their diet recommendations, and whether further invasive testing (MBSS or FEES) is indicated.

Subsequently, the SLP can perform additional testing including specific maneuvers. The results of these additional tests will be recorded in the CRF. The SLP will then document their diet recommendations that include the knowledge gained from the additional testing. Again the SLP will document whether further invasive testing (MBSS or FEES) is indicated.

Based on these recommendations, the patient will be allowed to advance their diet prior to the performance of the FEES, if indicated.

The coordinator should make sure that the BSE CRF is completely filled out before the SLP who completed the test leaves the ICU.

The BSE form for consistency testing is attached as Appendix.

3. FEES examination: The SLP will review the subject's medical record and become knowledgeable with the patient's medical history. The FEES examination will be performed by a second SLP who is blinded to the results of the BSE. The FEES should be performed within approximately 4 hours of the BSE.

Similar to the BSE, the patient should be seated with the head of the bed as elevated as possible. At the discretion of the SLP/investigator, Afrin and Lidocaine spray can be administered into the nasal passage before the laryngoscope is inserted. The use of these medications will be noted in the case report form.

Part 1: First the SLP will perform and videotape the examination of the upper airway. Velar closure, base of the tongue retraction, laryngeal elevation, right and left vocal cord/arytenoid mobility, right and left pharyngeal wall medialization, epiglottic retroflexion, granuloma formation, and upper airway edema will be assessed.

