Part 3: Three Ounce Water Swallow Test (3-WST): During the standardized 3-WST, patients receive three ounces of water and are instructed to drink the entire amount, via cup or straw, completely and without interruption (the cup can be held to the patient's mouth by the SLP).^{74;76;109} The 3-WST will be scored based on the PAS scoring system.

The results of the different components of the FEES assessment will be made available to the treating team if requested.

The coordinator should make sure that the FEES CRF is completely filled out before the SLP who completed the test leaves the ICU. See Appendix for FEES evaluation form.

4. Outcome Assessments

All patients will be followed for the subsequent outcome assessments.

Date of ICU discharge

ICU length of stay

Date of hospital discharge

Hospital length of stay

Discharge location

Reintubation since enrollment

If yes, date of reintubation

Died during ICU stay

Died during hospital stay

Surgical feeding tube placed?

5. Statistical analysis for Aim #1: Recursive partitioning or Classification and Regress Tree (CART)

analysis creates a tree that asks a series of yes/no questions, taking the user down different branches depending on the answers. At the end of each branch will be an estimated probability of outcome.

Statistically, recursive partitioning is a non-parametric approach to regression, in this case logistic regression.

We will predict a class Y (aspiration vs. non-aspiration) based on the predictor variables, X₁...X_n which can be either categorical or continuous. The main characteristic of this method is that predictor variables are “split” and partitions are created so that observations with the same response variable are grouped together.

After the first split, further splits of variables will occur based on the groups which are made from the prior split separately. The goal is to group observations with the same response class minimizing

misclassification. Some of the benefits of using recursive partitioning are that the splits are data driven, predictor variables can be used multiple times, and interactions will be included without having to decide which interactions are important. An algorithm (or tree) is obtained that splits the predictor variables until each person has been classified as with aspiration or non-aspiration in a terminal node. Pruning of the tree will take place by determining a value of the change in misclassification rate which is deemed too small to

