Consistent with the above ethical sensibilities regarding the participation of decisionally incapable subjects in research and the previous assessment of risks and benefits in the previous section, the present study presents a balance of risks and potential direct benefits that is *similar* to that available in the clinical setting.

ADDITIONAL SAFEGUARDS FOR VULNERABLE SUBJECTS

The present research will involve subjects who might be vulnerable to coercion or undue influence. As required in 45 CFR 46.111(b), we recommend that additional safeguards be included to protect the rights and welfare of these subjects. Such safeguards might include, but are not limited to: a) assessment of the potential subject's capacity to provide informed consent, b) the availability of the LAR to monitor the subject's subsequent participation and withdrawal from the study; c) augmented consent processes. The specific nature of the additional safeguards will be left to the discretion of the central IRB, in conjunction with the sites.

CONFIDENTIALITY

Federal regulations at 45 CFR 46 111 (a) (7) requires that when appropriate, there are adequate provisions to protect the privacy of subjects and to maintain the confidentiality of data. To maintain confidentiality, all laboratory specimens, evaluation forms, and reports will be identified only by a coded number. The coded number will be generated by a computer, and only the study team will have access to the codes. All records will be kept in a locked, password protected computer. All computer entry and networking programs will be done with coded numbers only. All paper case report forms will be maintained inside a locked office. Study information will not be released without the written permission of the patient, except as necessary for monitoring by the National Heart, Lung, and Blood Institute, and the PETAL Clinical Coordinating Center.

ADVERSE EVENTS

SAFETY MONITORING

Assuring patient safety is an essential component of this protocol. Each participating investigator has primary responsibility for the safety of the individual participants under his or her care. The Investigators will determine daily if any adverse events occur during the period from enrollment through **study day 2** or ICU discharge, whichever occurs first.

The following adverse events will be collected in the adverse event case report forms:

- Serious adverse events

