If yes complete the following table.

Patient stopped 1+ times?	Patient failed to drink the entire amount?	Cough/Choking?	Change in Voice??	Change in Breath Sounds?	No signs of aspiration
 Yes  No					

RESULTS of 3 oz water test? PASS FAIL

Pass= drinks the entire amount without stopping (use your judgment), and without coughing, choking during or immediately after completion.

Fail = does not finish the total amount, stops 1+ times (for more than a few seconds), or has overt signs of aspiration immediately after swallowing

SUMMARY OF CLINICAL EXAM

Results:

Dysphagia detected? Yes/no (oral or pharyngeal)

Aspiration detected? Yes/no

Diet texture recommendations (circle one)

Solids: regular (NDD3) mechanical (NDD2) puree (NDD1) npo

Liquids thin nectar honey npo

Part 4: Scoring Sheet for the FEES Testing

R 21 FEES Evaluation Form		
Study ID:	Date:	Time:

MAKE SURE THE ENTIRE EXAMINATION IS VIDEOTAPED

Afrin spray used: **YES** **NO**

Topical lidocaine used: **YES** **NO**

Velar Closure (hiss like a snake)	 Complete  Incomplete  N/A
Base of Tongue Retraction (Paul is tall)	 Present  Absent  N/A
Right Vocal Cord/Arytenoid Mobility	 None  Mild  Moderate  Severe  N/A
Left Vocal Cord/Arytenoid Mobility	 None  Mild  Moderate  Severe  N/A
Glottic Closure (breath hold, cough, phonation)	 Complete  Incomplete  N/A
Laryngeal Elevation/ Arytenoid lift (glide with an “eee”)	 Present  Absent  N/A
Right Pharyngeal Wall Medialization	 Complete  Reduced  Absent  N/A
Left Pharyngeal Wall Medialization	 Complete  Reduced  Absent  N/A

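### FEES results go to the treating team only on request, and no FEES step, FEES form field or adverse event rule clearly requires aspiration (PAS of 6 or more) to be reported

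*Combined protocol and SAP*

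**What the plan says.** Two places in the combined protocol and SAP deal with release of FEES results.

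- Study Procedures, 3. FEES examination, after Part 3: "The results of the different components of the FEES assessment will be made available to the treating team if requested."
- Informed consent, key points, item 8: "Share these results with your doctors so they have the additional information and can use the information to potentially take better care of you". No condition is attached. Item 6 of the same list presents FEES as definitive and as a guide to how the patient should eat.

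On feeding, section 2 (Bedside Evaluation, Part 3) has the BSE speech-language pathologist (SLP) record diet recommendations and whether invasive testing is indicated. It then states: "Based on these recommendations, the patient will be allowed to advance their diet prior to the performance of the FEES, if indicated." The BSE form in the Appendix closes with a diet texture field.

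The Background section says that the proposed mechanisms of aspiration in these patients "increase the likelihood of silent aspiration that would not be routinely detected on a BSE". The primary outcome is a PAS of 6 or more on FEES, silent or not; silent aspiration is a PAS of 8.

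**The concern.** The protocol tests patients with an instrument that it regards as a gold standard, because the BSE is expected to miss some aspiration. Diet, however, may be advanced on the BSE. If the FEES result reaches the treating team only when someone asks for it, study staff may know that a patient aspirates while the clinicians directing the feeding do not.

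Silent aspiration matters most here, because nothing at the bedside need prompt a request. The protocol's own Background links aspiration, silent or not, with pneumonia and hospital mortality, and says that its consequences are greater in these patients because of reduced respiratory reserve. It also justifies surrogate consent partly by potential direct benefit. For FEES, that benefit depends largely on the result being used in care.

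**Working it through.** The plan gives no figure on this point, so there is none to reproduce. The check is of the text, with a short calculation for context.

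1. **The two sentences side by side.** Item 8 can be read in two ways. As a script line, it tells the patient that the doctors will receive the results, while the procedure obliges staff to provide them only if asked. As an instruction to staff (the same list contains other imperatives), it is an unconditional direction placed in the consent section, while the FEES section carries a conditional one. On either reading the two do not match.

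2. **FEES procedure.** The required steps are video recording, a PAS score for each trial, two physiological measures, and a coordinator check that the form is complete before the SLP leaves the ICU. Notifying the treating team is not among them.

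3. **FEES form (Appendix, Part 4).** As shown, it records airway findings, PAS, timing of penetration or aspiration, swallowing onset time, residue and the 3-ounce water test. It has no diet recommendation or notification field. The BSE form does have a diet field.

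4. **Adverse event rules.** They collect serious events, and non-serious events that are related to study procedures or of uncertain relationship. Assessments go to the medical monitor. Aspiration is listed among the risks of FEES, so an investigator could report it as an event, but no rule names a PAS of 6 or more and the treating team is not the recipient.

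5. **Text that makes sharing more likely.** Safety Monitoring: "Each participating investigator has primary responsibility for the safety of the individual participants under his or her care." Informed consent: "Permission to approach patients and/or LARs will be requested from the attending physicians", so the attending physician knows of the study and can ask. The BSE SLP also states whether FEES is indicated. None of these is a rule to report aspiration.

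6. **What harm would require.** Staff act neither on item 8 nor on their general duty, the team does not ask, and the diet is or has been advanced. The documents do not say how often these coincide.

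7. **Context: expected aspirators among 225 planned patients.** Formula: enrolment × aspiration rate.
   - At 44% (Significance, given there as an upper figure): 225 × 0.44 = 99.0.
   - At 50% (Preliminary Data, item 5): 225 × 0.50 = 112.5, about 113.
   - Pilot uncertainty, taking all 26 pilot patients as the denominator: 26 × 0.50 = 13. The exact (Clopper-Pearson) 95% limits for 13/26 are the 0.025 quantile of Beta(13, 14) and the 0.975 quantile of Beta(14, 13), that is 0.299 and 0.701. Times 225, these give 67.3 and 157.7, about 67 to 158.

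   The release rule covers the FEES results of all 225 patients. The figures above say only how many patients might have a result that matters for feeding.

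**The case against.** The strongest reply is that the duty already exists. If item 8 is an instruction to staff, it directs them to share every FEES result, and the sentence in the FEES section may merely add access to component detail on request. Nothing in that sentence forbids unprompted sharing. Investigators hold a general safety duty and attendings know of the study. The consent form is not in this copy and may contain a commitment. Many aspirators would also be restricted on the BSE anyway: in the earlier cohort, 74% of patients with moderate or severe dysphagia were kept NPO after the initial BSE. Finally, the point touches no primary outcome, accuracy estimate or sample size.

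Much of this stands. A reader might infer that the protocol withholds aspiration results from clinicians; the documents do not support that. A reader might also take 99 to 113 as the number fed with undisclosed aspiration. That is not supported either, since the figure includes patients whose results would be shared and patients kept off oral feeding. Nor is diet advancement before FEES a product of the release rule: it is permitted separately, at a time when no FEES result exists.

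What does not stand is the conclusion that the wording can be left alone. A possible reading of a consent talking point is a weak basis for a safety report when the operative section states a narrower rule. Staff who follow the FEES section as written can complete every step without telling anyone.

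**Conclusion.** The point holds as a gap in a stated rule. FEES results are released on request, the consent talking points say something broader, and no FEES step, FEES form field or adverse event rule clearly requires a PAS of 6 or more to be reported to the treating team. The consequence is possible rather than shown: a patient with silent aspiration on FEES could go on being fed on the BSE recommendation without the team knowing.

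The frequency is not estimable from the documents. The 99 to 113 expected aspirators are background and carry no weight for severity. The conclusion rests on the procedure, forms and safety sections as supplied. A clear commitment in the consent form would strengthen the case for alignment, but would not itself put the step into the procedure. Confidence is medium. The change should be made, because the possible harm is serious and the remedy is small.

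**What to change.** Replace the release sentence in section 3 (FEES examination) with:

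> Once both the BSE and FEES forms are complete (or the second exam is cancelled), the FEES examiner or coordinator will promptly report any PAS score of 6 or more, with the consistency involved, to the treating team. If the FEES examiner judges that the patient is at immediate risk, the report is made at once and the early report is recorded on the form. Other FEES results are available on request after both forms are complete. If later video scoring changes a result to PAS 6 or more while the patient is still in hospital, that is also reported.

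Align item 8 of the consent talking points, and the consent form if it differs.

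The default waits for both forms because exam order is randomized and the BSE begins with a chart review: "The SLP will review the subject's medical record and become knowledgeable with the patient's medical history." A FEES report entered earlier could be seen before a BSE done second. The same reason applies to other results on request. The clause on video scoring is needed because recordings are shared between sites for scoring by investigators (Risks and Justifications).

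Costs:
- One notification step, by staff already present for scoring and form checks.
- When FEES is first, a wait of about 4 hours (the protocol's target interval between exams), unless the safety exception applies.
- When the exception is used, which should be rare, the BSE may no longer be independent of the FEES result. Recording the early report lets those patients be identified.
- Reporting could influence the descriptive follow-up outcomes (feeding tube, reintubation, length of stay).

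No planned Aim 1 or Aim 2 analysis changes, and no visit, procedure or staff is added. The change does not address diet advancement before a FEES result exists.
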